	• If the AE resolves to grade 1 or baseline level within 7 days, the drug can be resumed at the original dose;						
	• If the AE resolves to grade 1 or baseline level within 7 days, the drug can be resumed at a lower dose level;						
	If the AE occurs for the second time, regardless of the time of resolving to grade 1 or baseline level, the drug can be resumed at a lower dose level.						
	After reducing the dose, if AE remains grade 1 or baseline level for at least 2 consecutive cycles (56 days), the dose can be increased by one level.						
Grade 3	Symptomatic and supportive treatment						
	Withhold the invstigational drug for at least 7 days or until the AE resolves to grade 1 or baseline level (28 days at most).						
	• Resume medication at a lower dose level.						
	After reducing the dose, if AE remains grade 1 or baseline level for at least 2 consecutive cycles (56 days), the dose can be increased by one level.						
Grade 4	Discontinuation of study treatment. After the investigator evaluates and discusses with the sponsor, for non-life-threatening adverse events, medication can be continued.						
Any Grade	Stevens-Johnson syndrome						
	If patients have Stevens-Johnson syndrome (SJS), the investigational drug must be discontinued permanently. Patients should be sent to hospital immediately to receive clinical assessment and supportive treatment according to institutional guidance. Because there is risk of recurrence of SJS, the investigational drug should not be administered again.						

Table 7 Handling of dermatological toxicity and joint pain/myalgia and principles of dose adjustment

Severity of AE	Handling of AE and dose adjustment principles*
Grade 1 (systolic BP 120-139 mmHg,	Start blood pressure monitoring;
diastolic BP 80-89 mmHg)	The original dose was continued.

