Grade 2 (systolic blood pressure 140 - 159 mmHg, diastolic blood pressure 90 - 99 mmHg or elevation > 20 mmHg (diastolic blood pressure), with accompanying symptoms or elevation of previous normal blood pressure to 140 / 90 mmHg)	
 
Adopt antihypertensive therapy to make diastolic blood pressure ≤ 90 mmHg or systolic blood pressure 140 ≤ mmHg.
 
If previous blood pressure is in the normal range, monotherapy can be adopted;
 
If the subject has previously adopted antihypertensive therapy, the dose should be increased;
 
The original dose was continued.
 
If the blood pressure elevates by > 20 mmHg (diastolic blood pressure) and there are accompanying symptoms, the treatment should be withheld until symptom resolution or diastolic blood pressure ≤ 90 mmHg;
 
Medication can be resumed at the original dose.
 

Grade 3 (systolic blood pressure ≥ 160 mmHg, diastolic blood pressure ≥ 100 mmHg) or one additional drug required or more aggressive treatment required	
 
Adopt antihypertensive therapy to make diastolic blood pressure ≤ 90 mmHg or systolic blood pressure 140 ≤ mmHg.
 
Initiation of antihypertensive therapy and/or
 
Increase the intensity of antihypertensive treatment and/or
 
Add additional antihypertensive therapy
 
If there are accompanying symptoms, the treatment should be withheld until diastolic blood pressure ≤ 90 mmHg and/or systolic blood pressure ≤ 140 mmHg and symptom resolution;
 
Medication can be resumed at the original dose.
 
If the blood pressure is inadequately controlled after adding one drug or enhancing antihypertensive therapy, the dose should be reduced by one level;
 
If grade 3 hypertension occurs again, regardless of whether the dose has been reduced or antihypertensive therapy has been adopted, the dose should be reduced by one level again.
 

Grade IV (life threatening)	Handle according to treatment principles of local hospital;
	Discontinue the treatment with the investigational drug.

\* If the blood pressure can be stably controlled within one cycle, the dose can be increased after investigator assessment.

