## Table 9 Treatment of AEs except for dermatological toxicity and joint pain/myalgia and hypertension and principles of dose adjustment

Severity of AE	Handling of AE and dose adjustment principles
Grade 2 weight loss or other grade 3 or 4	
 
Withhold treatment until the AE resolves to grade 1 or baseline level;
 
Reduce by one dose level;
 

AEs	
 
If the subject can tolerate the reduced dose level and the same AE does not occur for at least 3 consecutive cycles, the former dose level can be restarted;
 

Severity of AE	Handling of AE and dose adjustment principles					
Asymptomatic grade	Monitor clinical symptoms closely and continue medication at the original dose;					
3 or 4 laboratory abnormality	If related clinical symptoms are accompanied, treatment with the investigational drug should be withheld.					
(including CPK and lipase) for $\leq 10$ days	f the investigator considers after evaluation that medication should be restarted for the patient's benefit, it is necessary to discuss with the sponsor to decide whether to restart medication.					
Asymptomatic grade 3 or 4 laboratory	Monitor clinical symptoms closely; for grade 4 AEs, the treatment should be withheld until the AE resolves to grade 3;					
abnormality (including CPK and lipase) for > 10 days	• For asymptomatic CPK and lipase increased, the treatment does not need to be withheld;					
	Once the AE resolves to grade 3, the drug can be resumed at the original dose or a lower dose level as per the decision of the investigator and the sponsor.					
Clinically significant grade 3 or 4	If related clinical symptoms are accompanied, treatment with the investigational drug should be withheld.					
laboratory abnormality (including CPK and lipase) for > 10 days	If the investigator considers after evaluation that medication should be restarted for the patient's benefit, it is necessary to discuss with the sponsor to decide whether to restart medication.					

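### Table 8's Grade 2 hypertension hold can be lifted on diastolic pressure alone while the patient is still symptomatic, and for baselines of 69 mmHg or less that condition can already be met when the hold starts

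*Combined protocol and SAP*

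**What the plan says.** All the relevant text is in section 5.3.2 and its Table 8 on hypertension.

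- **Grade 1.** The diastolic band is "diastolic BP 80-89 mmHg", and dosing continues unchanged.
- **Grade 2, definition.** Besides the absolute bands (systolic 140 to 159, diastolic 90 to 99), a patient qualifies by "elevation > 20 mmHg (diastolic blood pressure), with accompanying symptoms". This is an alternative to the absolute bands, so a patient can be Grade 2 with a diastolic below 90.
- **Grade 2, action.** The original dose is normally continued with antihypertensive treatment. If diastolic has risen by more than 20 mmHg and there are symptoms, "the treatment should be withheld until symptom resolution or diastolic blood pressure ≤ 90 mmHg". The row then adds: "Medication can be resumed at the original dose".
- **Grade 3, hold.** For symptomatic patients, "the treatment should be withheld until diastolic blood pressure ≤ 90 mmHg and/or systolic blood pressure ≤ 140 mmHg and symptom resolution". Symptom resolution is part of the release.
- **General text of 5.3.2.** Resumption at the dose in use when the event occurred is allowed once the event has resolved to grade 1 or baseline. If that is not reached within 28 days, treatment stops unless the investigator judges the event not clinically significant. The investigator may also suspend treatment at any time for intolerable toxicity.

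**The concern.** The hold has two entry conditions, a relative rise and symptoms. One of its two alternative exits is an absolute diastolic value that checks neither. A patient with a low baseline can therefore enter the hold without ever exceeding 90 mmHg. A site that reads the row literally has a satisfied release condition on the day the hold begins, and permission to return to full dose, while the symptoms that prompted the hold continue.

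At stake is the protection of individual patients. Blood pressure is a signal that the protocol itself follows: section 1.2.1.1.1 reports a diastolic rise in dogs after a single dose, without a systolic change, and promises close monitoring in the trial. The same section adds that the finding does not mean severe toxicity, so the signal should not be overstated. Exclusion criterion 5 in section 4.2 removes uncontrolled hypertension, but that does not touch patients with a low baseline diastolic.

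**Working it through.** The plan gives no figure to reproduce. The check enumerates the rule in whole mmHg.

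**Inputs (Table 8).** Trigger: rise > 20, so onset diastolic ≥ b + 21 for baseline b, with symptoms. The onset value is kept below the Grade 3 diastolic range, so ≤ 99. Pressure limb of the release: diastolic ≤ 90.

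**Step 1: which baselines can trigger the hold?** b + 21 ≤ 99 gives b ≤ 78.

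**Step 2: when is the release already true at onset?** b + 21 ≤ 90 gives b ≤ 69. On a continuous scale the bound is b < 70.

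**Step 3: counts.** Possible onset values: 99 − (b + 21) + 1 = 79 − b. Those already at or below 90: 90 − (b + 21) + 1 = 70 − b, or zero if negative.

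| Baseline diastolic | Possible onset values | Release already met |
|---|---|---|
| 60 | 19 (81–99) | 10 (81–90) |
| 65 | 14 (86–99) | 5 (86–90) |
| 69 | 10 (90–99) | 1 (90) |
| 70 | 9 (91–99) | 0 |
| 78 | 1 (99) | 0 |

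These count grid points and are not probabilities.

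**Step 4: baselines 70 to 78.** Onset lies between 91 and 99, so a fall of 1 to 9 mmHg to 90 meets the release. At 90 the rise is 90 − b, that is 20 down to 12, so the rise part of the trigger has lapsed. The symptom part has not been tested.

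**Step 5: compare with the general rule.** Take 65 rising to 88, still symptomatic. The rise is 23 with symptoms, so the patient still meets the Grade 2 definition and has not resolved to grade 1 or baseline. The general text withholds same-dose resumption; the row permits it. For baselines of 70 to 78 the general rule helps less. Once diastolic is 89 or lower, the rise is at most 19 and the value lies in the Grade 1 band or below, so on diastolic grading the event can count as resolved with symptoms present.

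**Step 6: after the fix.** If release requires symptom resolution, no patient can meet it at onset at any baseline, because symptoms are part of the trigger.

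**Frequency.** The documents give neither a rate of symptomatic Grade 2 hypertension nor a baseline blood pressure distribution. A loose ceiling comes from section 1.3.1.1.2. Hypertension is absent from the list of events at 25% or more among the 85 ripretinib patients, so at most 21 of 85 had it at any grade (0.25 × 85 = 21.25). If that rate carried over, 35 × 21/85 = 8.6 subjects. The affected group also needs symptoms, a rise above 20 mmHg and a baseline of 78 or less, so it should be smaller.

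**The case against.** The strongest reply is that Table 8 sits inside 5.3.2 and must be read with it. The general rule does protect the patient who goes from 65 to 88. That stands, and it turns the point into a conflict between two texts. It does not remove the point: no sentence gives either text precedence, the table is the more specific, and a site grading by band alone could place 88 in Grade 1 and consider both rules met.

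Second, withholding until a condition is met presupposes that the condition is not yet true, so for a patient already at or below 90 symptom resolution must be the working limb. This is a sensible reading, but the row does not state it, and it does nothing for baselines of 70 to 78.

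Third, looser release at a lower grade is ordinary graduated design. Table 7 continues dosing through Grade 2 skin and joint events unless they fail to improve within 7 days. This is fair: the protocol does not treat every symptomatic Grade 2 event as a bar to dosing. Here, however, the row itself orders a hold because of symptoms, and an exit that ignores them defeats that purpose.

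Fourth, the connective may be a translation slip. The English text has others nearby, so this is plausible and cannot be settled from the documents.

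A reader might also infer that the rule compels re-dosing or endangers many subjects. The documents do not support either inference. Resumption is permitted rather than required, suspension is allowed at any time, and no rate is given that would show more than a few cases.

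**Conclusion.** The Grade 2 row is wrong as written, as a minor safety rule. Its release condition can be true at onset for any baseline diastolic of 69 mmHg or less. For baselines of 70 to 78 it can become true after a fall of at most 9 mmHg with symptoms unchanged. In both cases the row permits the original dose in a still-symptomatic patient. For the low-baseline patient this contradicts the general rule in 5.3.2, and precedence is not stated.

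The conclusion assumes whole-mmHg readings, an onset diastolic below 100, and an English connective that reflects the operative text. Few subjects are likely to be affected, though the documents allow only a loose ceiling. It would go too far to infer any consequence for the primary endpoint, sample size or error rates; none follows from this row.

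**What to change.** Reword the Grade 2 row so that the hold is lifted only when symptoms have resolved, matching the requirement already in the Grade 3 row. State that the 5.3.2 condition of resolution to grade 1 or baseline still applies to same-dose resumption. First check the connective against the Chinese text; if the slip is only in the translation, correcting the English version is enough.

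Two tempting alternatives are worse. Requiring both symptom resolution and diastolic of 90 or less within the row would keep holding a symptom-free patient at 91 to 99, a pressure at which the same row otherwise continues the original dose. A sentence making Table 8 override 5.3.2 would remove the protective general rule, and should not be added unless the row has been corrected.

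The cost is one edit in one table, with no extra visits or tests. The downside is that some holds last slightly longer.

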## Table 9 Treatment of AEs except for dermatological toxicity and joint pain/myalgia and hypertension and principles of dose adjustment

Severity of AE	Handling of AE and dose adjustment principles
Grade 2 weight loss or other grade 3 or 4	
 
Withhold treatment until the AE resolves to grade 1 or baseline level;
 
Reduce by one dose level;
 

AEs	
 
If the subject can tolerate the reduced dose level and the same AE does not occur for at least 3 consecutive cycles, the former dose level can be restarted;
 

Severity of AE	Handling of AE and dose adjustment principles					
Asymptomatic grade	Monitor clinical symptoms closely and continue medication at the original dose;					
3 or 4 laboratory abnormality	If related clinical symptoms are accompanied, treatment with the investigational drug should be withheld.					
(including CPK and lipase) for $\leq 10$ days	f the investigator considers after evaluation that medication should be restarted for the patient's benefit, it is necessary to discuss with the sponsor to decide whether to restart medication.					
Asymptomatic grade 3 or 4 laboratory	Monitor clinical symptoms closely; for grade 4 AEs, the treatment should be withheld until the AE resolves to grade 3;					
abnormality (including CPK and lipase) for > 10 days	• For asymptomatic CPK and lipase increased, the treatment does not need to be withheld;					
	Once the AE resolves to grade 3, the drug can be resumed at the original dose or a lower dose level as per the decision of the investigator and the sponsor.					
Clinically significant grade 3 or 4	If related clinical symptoms are accompanied, treatment with the investigational drug should be withheld.					
laboratory abnormality (including CPK and lipase) for > 10 days	If the investigator considers after evaluation that medication should be restarted for the patient's benefit, it is necessary to discuss with the sponsor to decide whether to restart medication.					

## 5.4 Drug Packaging and Labeling

DCC-2618 provided by the sponsor is tablets, 50 mg/tablet, and will be packaged in high density polyethylene bottles sealed with child-resistant closures, 30 tablets/bottle.

Drug label will be prepared according to regulations.

## 5.5 Drug storage

DCC-2618 must be stored at 5 - 25 °C (41 - 77 F). Seal up, protected from light and moisture (such as places close to shower of the bathroom). The allowed storage temperature range is 2 - 27 °C (35.6 - 80.6F).

Study sites should store the drugs at safe places with temperature monitoring and can obtain the drugs after obtaining authorization.

#### 5.6 Medication compliance

In order to ensure subjects' compliance, the investigator or designated personnel should supervise all administrations at the site. At each visit, the investigator or designated personnel should review subject compliance and remind subjects of medication requirements.

If subject compliance is poor and not improved after education and training, the treatment should be discontinued.

## 5.7 Responsibilities for Reception, Storage, and Management of Investigational Drugs

It is the responsibility of the investigator to manage the investigational products and equipment on its study site that are provided by the sponsor. The investigational products and supplies must be recorded accurately in accordance with the protocol and national laws and regulations, supplied as required by the study at any time and maintained, stored, dispensed, used and disposed according to the regulations. The investigator should designate a person to receive, store, dispense and return all investigational drugs during the study, and to record the dispensing accurately. Drug dispensing management form should include subjects' identification number, quantity of the drugs and drug bottles dispensed and returned. The return of the drug from the subject to the study site should be marked as "returned" to separate from the drug not yet dispensed.

All dispensing and management records should be accessible to the Sponsor for review. Study monitors will verify according to drug dispensing management form and stored drugs. Designated drug managers will dispense the investigational drugs according to the study protocol and drug management manual and cooperate with monitors' audit.

## 5.8 Drug Recovery and Destruction

Subjects should be instructed to return all used and partially used drug bottles. The investigator or the designated personnel should correctly record all dispensed and returned investigational drugs, including date, quantity and patients who used the drug. Unused investigational drugs should be uniformly returned after the end of study to the sponsor for uniform destruction.

## 5.9 **Prior and Concomitant Medications**

## 5.9.1 **Previous treatments**

Previous treatments (including drug therapy and non-drug therapy and surgery) should be recorded from 30 days prior to signing the informed consent form and recorded in the original medical record and eCRF.

## 5.9.2 **Prior Anti-Cancer Therapy**

Any prior anti-tumor therapies should be recorded in the original medical record and eCRF.

## 5.9.3 Concomitant medication

All concomitant medications during the study, including vitamin supplementation, nonprescription medication and herbal medicines (generic name of drug, administration purpose, administration dose and time, etc.) must be recorded in the original medical record and the eCRF in detail from the date of the first dose to 30 days after the last dose.

## 5.9.3.1 Drugs Allowed to be Used

Subjects can use drugs for improving symptoms (e.g., analgesics, laxative and antiemetics).

Drugs (e.g., antacid) for increasing pH value of gastric juice are allowed to be used , as long as they are not used within 2 hours before and after taking the investigational drug.

## 5.9.3.2 Drugs to be avoided or used with caution

The following drugs should not be used or used with caution:

- Potent or moderate inhibitors or inducers of CYP2D6, CYP2C8 or CYP2E1. For related drugs, please refer to the website of the Indiana University, School of Medicinehttp://medicine.iupui.edu/clinpharm/ddis/main-table/
- Known substrates or inhibitors of P-glycoprotein 1 (permeability glycoprotein, also known as multidrug resistance protein 1 or MDR1). Refer to the website of FDA for related inhibitors: https://www.fda.gov/Drugs/DevelopmentApprovalProcess/DevelopmentResourc es/DrugInteractionsLabeling/ucm093664.htm#table5-2 and https://www.fda.gov/Drugs/DevelopmentApprovalProcess/DevelopmentResourc es/DrugInteractionsLabeling/ucm093664.htm#table5-1 for MDR1.
- Known substrates of OATP1B1 and OATP1B3. Refer to FDA website for related drugs:

https://www.fda.gov/Drugs/DevelopmentApprovalProcess/DevelopmentResourc es/DrugInteractionsLabeling/ucm093664.htm#table5-1

• Drugs metabolized through CYP2C8, CYP2C9, CYP2C19 or CYP2D6. For related drugs, please refer to the website of the Indiana University, School of Medicine: http://medicine.iupui.edu/clinpharm/ddis/main- table/

For example:

- Warfarin can be used under close monitoring since the investigational drug has an inhibitory effect on CYP2C9.
- Clopidogrel should be avoided. The activity of clopidogrel should be dependent upon CYP2C19. The efficacy of clopidogrel may be reduced if combined with the investigational drug.

Considering that taking the investigational drug and the above drugs simultaneously may have potential drug interaction, any of the above drugs should be taken under close monitoring.

## 5.9.3.3 Prohibited Drugs

Some drugs and foods are prohibited from the start of the screening period to the end of

safety follow-up in this study. The following drugs should be prohibited:

- Potent or moderate inhibitors or inducers of CYP3A4, including some herbal medicines (e.g., St. John's wort), should be discontinued 14 days or 5 x half-life prior to the first dose of the investigational drug (whichever is longer). For related drugs, please refer to the website of the Indiana University, School of Medicine: http://medicine.iupui.edu/clinpharm/ddis/main-table/
- Grapefruit or grapefruit juice should be discontinued 14 days prior to the first dose of the investigational drug.
- Known substrates or inhibitors of BCRP transporter should be discontinued 14 days or 5 x half-life prior to the first dose of the investigational drug (whichever is longer). For related drugs, please refer to FDA website: http://www.fda.gov/Drugs/DevelopmentApprovalProcess/DevelopmentResource s/DrugInteractionsLabeling/ucm093664.htm
- Anti-tumor therapy, including investigational treatment, should be discontinued 14 days or 5 x half-life prior to the first dose of the investigational drug (whichever is longer). For prior biological therapies, eg, monoclonal antibodies with a half-life longer than 3 days, the interval must be at least 28 days prior to the first dose of investigational drug.

## 5.9.4 Accompanying treatment

All treatment operations must be recorded in the original medical record and the eCRF in detail from the date of the first dose to 30 days after the last dose.

Surgical resection or palliative radiotherapy during the study (including the intensive blood collection period) should not be conducted before communication with the Sponsor. If the investigator or the sponsor considers this meets subjects' best benefit, surgical resection or palliative radiotherapy can be performed. However, in PFS analysis, subjects should be deleted.

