## 1.3.1.3.2 Study DCC-2618-03-001

Only efficacy data (n = 129) in the double-blind stage as of 31 May 2019 are listed. The median (95% CI) of PFS in the ripretinib group was 27.6 (20.0, 29.9) weeks and that in the placebo group was 4.1 (4.0, 7.3) weeks. Risk of disease progression or death in patients who received ripretinib treatment decreased by 85%, showing statistically significant difference with the placebo group (HR 0.15; stratified log-rank test P < 0.0001). At week 26, 51.0% of patients receiving ripretinib treatment and 3.2% of patients receiving placebo didn't have disease progression (estimated PFS rate).

Confirmed ORR was 9.4% in the ripretinib group and 0% in the placebo group (P = 0.0504, Fisher's exact test); however, statistical significance was not reached.

OS results of the placebo group included OS data of patients in the placebo group who

received ripretinib treatment crossly after IRR-assessed disease progression. During the final analysis, 29 patients (65.9%) in the placebo group were subject to crossover treatment in the treatment group and received at least one dose of ripretinib. Of 85 patients in the ripretinib group, 26 patients (30.6%) experienced OS events and 59 patients (69.4%) were censored. Of 44 patients in the placebo group, 26 patients (59.1%) experienced OS events and 18 patients (40.9%) were censored.

The median (95% CI) of OS in the ripretinib group was 65.6 (53.6, 65.6) weeks and that in the placebo group was 28.6 (17.9, 50.4) weeks. Compared with those in placebo group, the risk of death in patients receiving ripretinib decreased by 64% (HR 0.36; stratified log-rank test P = 0.0004).

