# 9.1 Determination of sample size

This phase 2 bridging study is to prove the efficacy of DCC-2618 in Chinese patients is consistent with or similar to that in global patients using the primary endpoint of progression-free survival (PFS) on the basis of independent radiologic review.

Standard definition of bridging study success (consistent or similar): mPFS of ripretinib in Chinese patients will be statistically longer than 1 month, that is, the lower limit of bilateral 90% confidence interval of the observed mPFS is longer than 1 month. Statistical hypothesis: H0: mPFS is 1 month; Ha: mPFS is 2.5 months; bilateral significant level is 0.1; assumed enrollment duration is 6 months; follow-up duration is 2 months; drop-out rate is 15% under at least a 90% test power; approximately 35 subjects should be enrolled to meet the test purposes.

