#### 9.3 Analysis data sets

1) Intent-to-treat (ITT) - Subjects having signed the Informed Consent Form and been included in the trial.

- 2) Full analysis set (FAS): All patients who use at least one dose of the investigational drug.
- 3) Safety set (SS): All patients receiving at least one dose of the investigational drug. In the study, the definition of SS is consistent with FAS. SS is the main population for safety indicator analysis.
- 4) Efficacy analysis set (EAS): all subjects who enter the treatment period and have received at least one dose of the investigational drug, that is, all the patients who have started to receive continuous treatment with the investigational drug since C1D1.
- 5) PK analysis set: all subjects who received at least one dose of the investigational drug and have at least one blood concentration data of DCC-2618 or DP-5439 after administration.
- 6) Per protocol population (PP): subjects in FAS population who do not have expected protocol violations influencing efficacy and/or safety assessment (e.g., the enrolled patient does not comply with critical qualification criteria). Definition of per protocol population will be confirmed before database locking. The PP-based analysis will support the FAS-based analysis.

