#### 9.4.2 Subject disposition

All subjects who enter this study (that is, signing informed consent forms) will be summarized. In addition, number of subjects of each analysis data set and number of subjects deleted from each data analysis set (FAS, safety and PP, if applicable) will be summarized. Number and percentage of subjects who finish the study and number and percentage of subjects who withdraw from the study and reasons for drug withdrawal will be summarized.

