## 9.4.5 Efficacy analysis

# 9.4.5.1 Primary endpoints:

# PFS analysis based on independent radiology review

PFS based on independent radiologic review is defined as the time from the first dose of investigational drug (C1D1) to the first documentation of disease progression based on independent radiologic review or death due to any cause (whichever occurs first). Subjects who have previously received surgery for target lesion or non-target lesion, those who have previously received other anti-tumor treatments, and those whose progression or death date is not recorded for any reasons will be censored on the day of the last assessment.

EAS will be used as the main analysis set, with PP as the supporting analysis set. Sensitivity analysis of progression-free survival will be performed, which will be further described in SAP.

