## 9.4.5.4 Exploratory endpoint

PFS2 based on investigator's assessment: it is defined as the period from the first dose of investigational drug (150 mg, BID) to the first documented tumor progression or death from any cause (whichever is the first) after the dosage is increased to 150 mg (BID). Subjects who have previously received surgery for target lesion or non-target lesion, those who have previously received other anti-tumor treatments, and those whose progression or death date is not recorded for any reasons will be censored on the day of the last assessment. For patients who are not assessed after dose increase, the date of the first dose of the investigational drug (150 mg, BID) will be taken as the censoring date.

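### The protocol gives two incompatible rules for on-study surgery or radiotherapy in the primary PFS analysis, and the censoring rule is not tied to the procedure date

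*Combined protocol and SAP*

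**What the plan says.** - **Section 5.9.4** allows surgical resection or palliative radiotherapy during the study, after communication with the sponsor, and ends: "However, in PFS analysis, subjects should be deleted".
- **Section 9.4.5.1** lists the patients to be censored in the primary IRR-based PFS analysis. It begins "Subjects who have previously received surgery for target lesion or non-target lesion, those who have previously received other anti-tumor treatments" and says they "will be censored on the day of the last assessment". The EAS is the main analysis set.
- **Section 9.3** defines the EAS as "all subjects who enter the treatment period and have received at least one dose of the investigational drug", with continuous dosing from C1D1. It makes no exclusion for on-study procedures.
- **Section 9.4.2** uses the same verb as 5.9.4 for removal from a population: "number of subjects deleted from each data analysis set".
- **Section 9.4.5.4** repeats the 9.4.5.1 censoring wording for PFS2. It adds a fallback date, the first 150 mg BID dose, for patients with no assessment after the dose increase.
- **Section 9.1** defines success as follows: "the lower limit of bilateral 90% confidence interval of the observed mPFS is longer than 1 month".

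**The concern.** A patient cannot be both removed from the PFS analysis and kept in it as censored. Two analysts following different sections would report different primary results.

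Deletion selects patients on a post-baseline event. Treatment may continue after IRR progression (sections 3.1 and 6.10.1), and 5.9.4 covers any procedure during the study. As worded, a progression already recorded could be lost because of a later procedure, which favours success. Deleting patients who were still progression-free works the other way.

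The censoring rule has two gaps of its own:

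1. **No time anchor.** Inclusion criterion 3 requires earlier imatinib, sunitinib and one or two other drugs, so taken literally every patient has previously had other anti-tumor treatment. Treatment after C1D1 and before progression is evidently meant, but not written.
2. **No procedure-linked date.** A patient who stays on drug after a resection keeps having scheduled scans. Censoring at the last of them counts event-free time after a lesion has been removed.

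Radiotherapy is not named in 9.4.5.1. It may fall under other anti-tumor treatment, since section 6.9 lists radiation among the anti-neoplastic therapies.

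**Working it through.** **1. The plan's own sample size.** Section 9.1 gives H0 median 1 month, Ha median 2.5 months, two-sided alpha 0.10, power 90% and drop-out 15%. Assume exponential PFS and test S(1 month):

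- S0 = 0.50 and S1 = 0.5^(1/2.5) = 0.758.
- n = [(1.645·√(0.5·0.5) + 1.282·√(0.758·0.242)) / (0.758 − 0.5)]² = 28.3, rounded up to 29.
- 29 / 0.85 = 34.1, rounded up to 35, as planned.

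With the same formula, power is 91.4% with no deletions, 90.6% with one, 89.8% with two, 88.9% with three and 86.9% with five.

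**2. The success boundary.** With no censoring before 1 month, the lower 90% limit of the median exceeds 1 month when the lower limit of S(1 month) exceeds 0.5. I assume the log-log limit: exp{−exp[ln(−ln S) + 1.645·se]}, with se = √(d/(n(n−d))) / |ln S|.

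For 12 events in 35, S = 0.657, se = 0.291 and the lower limit is 0.508.

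| Events by 1 month / n | Lower 90% limit of S(1) | Exact one-sided binomial p | Decision |
|---|---|---|---|
| 13/35 | 0.479 | 0.088 | fail |
| 11/33 (two recorded progressors deleted) | 0.513 | 0.040 | pass |
| 12/35 | 0.508 | 0.045 | pass |
| 12/34 (one progression-free patient deleted) | 0.495 | 0.061 | fail |

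**3. How likely a boundary result is.** The probability of an event by 1 month is p = 1 − 0.5^(1/median), with n = 35. The two longer medians come from section 1.3.1.3.2: "The median (95% CI) of PFS in the ripretinib group was 27.6 (20.0, 29.9) weeks". They convert to 4.60 months (20.0 weeks) and 6.35 months (27.6 weeks).

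| True median | Expected events by 1 month | P(12 or 13 events) |
|---|---|---|
| 2.5 months | 8.5 | 0.090 |
| 20.0 weeks | 4.9 | 0.0019 |
| 27.6 weeks | 3.6 | 0.0001 |

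**4. Effect on the reported median.** The documents give no procedure rate, so two rates were assumed. Simulation: 6000 trials, n = 35, exponential PFS, follow-up 5.5–11.5 months, scans at cycles 1–4 and then every second cycle, procedures independent of PFS. The 21-event cutoff in section 9 was not modelled. Each cell gives the lower / higher procedure rate.

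| Rule | Typical median, true 6.35 months (on average 1.9 / 4.0 procedures) | Typical median, true 2.5 months (2.7 / 5.6 procedures) | Success, true 2.5 months |
|---|---|---|---|
| All true events | 6.40 / 6.37 | 2.50 / 2.51 | 0.94 / 0.95 |
| Deletion | 5.99 / 5.70 | 2.26 / 2.07 | 0.85 / 0.75 |
| Censor at last scan before procedure | 6.33 / 6.23 | 2.46 / 2.43 | 0.92 / 0.90 |
| Censor at last scan of all | 6.57 / 6.77 | 2.59 / 2.69 | 0.94 / 0.95 |

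At 27.6 weeks, success is about 1.00 under every rule.

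**5. If procedures are informative.** A separate simulation (1,200 runs per scenario) assumed a true median of 1 month, a 20% procedure rate, early progressors three times as likely to have one, and a 2-month delay in progression. The success rate was 5.2% without procedures, 11.8% with deletion, 17.5% with censoring before the procedure and 49.4% with censoring at the last scan of all.

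**The case against.** - **Deleted may be a loose translation of censored.** The English is rough in places, and 5.9.4 names no analysis set. On that reading the two sections agree that surgery patients are censored. This cannot be excluded, but 9.4.2 uses the verb for removal from an analysis set and 9.4.5.1 uses the word censored separately. The missing anchor and date remain on either reading.
- **Section 9 defers detail to a SAP finalized before database lock.** Censoring dates are the kind of detail a SAP may settle. That does not reconcile two protocol sentences, and 9.4.5.1 expressly defers only the sensitivity analyses. In an open-label trial, a rule fixed that late could be chosen with outcomes visible.
- **The gaps are narrower than they look.** No analyst would censor every patient on the literal wording. For patients who stop treatment without progression, imaging ends at new anti-tumor therapy, so their last assessment already precedes it or nearly so. Both points stand. The date gap that matters is resection or radiotherapy in patients who stay on drug.
- **The numbers near the boundary are fragile.** The flip from 13/35 to 11/33 needs two early progressors with later procedures and erasure of their recorded events. Applying the 21-event cutoff at a 2.5-month median cuts procedures from 2.7 to 1.8, and success becomes 0.88 with deletion against 0.91 with all true events. The loss is then about 3 points, not 9. The 27.6-week medians barely change.
- **The proposed censoring rule is not free of bias.** In step 5 it gives more false success than deletion (17.5% against 11.8%). With a 10% rate the figures are 8.7% and 7.6%; with a 20% rate unrelated to prognosis, 7.7% and 3.0%. This stands, and is why a sensitivity analysis has to accompany it.

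**Conclusion.** The concern holds, and it should be fixed. Sections 5.9.4 and 9.4.5.1 cannot both be followed, and 9.4.5.1 as written can count time after a procedure as progression-free.

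The planned sample size of 35 is unaffected. The success decision is exposed only near the boundary: a 0.09 chance of such a result at the 2.5-month alternative, and a remote one near the global median. The more likely consequence is a shift of a few tenths of a month in the reported median, down with deletion and up with censoring at the last scan of all. That matters because section 1.4.1 rests the case on consistency with the global trial.

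These sizes rest on exponential PFS and assumed procedure rates. The contradiction does not depend on them.

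**What to change.** - **Section 5.9.4:** replace the deletion sentence with a cross-reference to 9.4.5.1.
- **Section 9.4.5.1:** state that patients who, after C1D1 and before IRR-documented progression or death, have a lesion resected, palliative radiotherapy or new anti-tumor therapy stay in the EAS. They are censored at the last tumor assessment before it, or at C1D1 if there is none. Progression or death already recorded before the procedure remains an event.
- **Section 9.4.5.4:** use the same wording, anchored to the first 150 mg BID dose and investigator-assessed progression. The existing fallback date stays.
- **SAP:** among the PFS sensitivity analyses, include one that counts these procedures or therapies as events.

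The cost is wording and one extra analysis run. The reported median may shift slightly in either direction, and no clinical rule changes.
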